# **PROTOCOL REVISIONS**

Revision Level	Changes Made to Protocol	Date	Ву
0.0	Original Release	02/28/2017	[name], [name], [name], [name], [name], [name], [name]
1.0	Amendment 1: Update to aims, statistical section, study procedures, and inclusion of international study interim analysis	03/16/2017	[name], [name], [name] [name]
2.0	Amendment 2: Increase study enrollment	9/18/17	[name], [name]

# GLOSSARY

**Actigraph:** A wrist-watch-like device placed on the wrist to measure motor activity. The device continually records movements and ambient light intensity. Collected data are downloaded to a computer and analyzed offline. Analysis of activity/ inactivity can be further analyzed to estimate sleep patterns.

**Apnea**: The cessation of airflow at the nostrils and mouth for at least 10 seconds as determined using nasal-oral thermistor, nasal pressure or device flow

**Apnea/Hypopnea Index (AHI):** The number of apneas and hypopneas per hour of sleep.

**Hypopnea**: Shallow breathing in which the air flow in and out of the airway is significantly reduced as detected by nasal pressure or device flow - often associated with oxygen desaturation of 4% or EEG arousal.

**Obstructive Sleep Apnea (OSA):** a disorder in which the airway collapses, either completely or partially, repeatedly during the night and is associated with desaturation, sleep fragmentation, and daytime sleepiness.

**Polysomnography (PSG):** Continuous and simultaneous recording of physiological variables during sleep, including EEG, EOG (the basic stage scoring signals). EEG (FPz-M1, F3-M2, F4-M1, C3-M2, C4-M1, O1-M2, O2-M1), EOG (E1-M2, E2-M2).

**PowerSleep device:** A wearable and non-invasive device, consisting of a silicone headband with 1 integrated electrode and headphones covered by speaker foam over each ear. The headband is connected via a tether cable to a user interface which houses the electronics of the device. The headband is adjustable via a Velcro strap. The device also includes a right mastoid electrode. EEG can be monitored and recorded by the PowerSleep device. Soft audio tones (below 65dB) can be administered via the speakers during deep sleep throughout the night.

**Sleep deprivation:** is defined by insufficient sleep to support adequate alertness, performance and health, either because of reduced total sleep time or fragmentation of sleep by brief arousals.

**Sleep restriction:** is also known as chronic sleep deprivation, and exists when the individual routinely sleeps less than required for optimal functioning.

**Slow Wave Activity**: is slow high-amplitude EEG oscillations which occur during Slow Wave Sleep.

**Slow Wave Sleep (SWS):** is the deepest stage of non-rapid eye movement (nREM) sleep. It is one of the two core sleep stages in mammals. SWS alternates with rapid-eye-movement (REM) sleep in a cyclical pattern. SWS is predominant during the early part of sleep and decreases in intensity and duration across the sleep period. SWS is known as deep sleep.

# I. BACKGROUND AND SIGNIFICANCE

Sleep is increasingly recognized as important to public health. Sleep insufficiency may be defined as a condition where sleep duration or/and sleep quality is insufficient to support adequate alertness, performance, and health [1]. Sleep insufficiency has been linked to motor vehicle crashes, industrial disasters, medical and other occupational errors, reduced quality of life and productivity and a higher risk of chronic diseases such as hypertension, diabetes, depression, and obesity, and cancer [2]. Sleep insufficiency may be caused by behavioral sleep restriction to meet the demands and opportunities of modern society, but may reflect non-restorative sleep due to shallow and/or fragmented sleep [2]. The Center for Disease Control examined the prevalence of "insufficient sleep or rest during the past month" among American adults [3]. After adjustment for age, the prevalence of "insufficient sleep or rest" ranged from 7.9% to 19.3% [4]. In 2009, an average of 35% of Americans within the age range of 35-<45yrs reported falling asleep unintentionally during the past month [4].

In individuals between the ages of 20-60 slow-wave sleep (SWS), the deepest stage of non-rapid-eye movement (NREM) sleep, comprises between 10 and 30% of total sleep time[5]. During SWS, high amplitude, low frequency oscillations, referred to as slow waves or delta waves, appear in the EEG [6]. Larger slow waves reflect deeper, more intense sleep that is less likely to be fragmented or interrupted[7]. When slow-wave activity (SWA) is acutely suppressed by arousal stimuli or total sleep deprivation, a rebound occurs during the recovery night.

A large body of evidence indicates that SWA is a pivotal component of the restorative effects of sleep for both the brain and the rest of the body [6, 8-24]. SWA has beneficial effects on memory and learning [25] as well as on hormonal function [26], glucose metabolism [9, 24, 27] and cardiovascular regulation [23, 28]. Experimental studies have shown that insufficient amounts of SWS lead to impaired alertness and cognitive performance [2, 29], obesity [30] and a higher risk of cardio and metabolic disease [11, 20, 31]. Low amounts of SWS are also typical of normal aging [5, 32-36], and of common sleep disorders such as obstructive sleep apnea [37] and insomnia [38]. Increasing the amount and intensity of SWS may have a wide range of beneficial effects on daytime function, quality of life and physical and mental health [2, 6, 33, 38-41].

Currently available sleeping medications, whether prescription or over the counter, have not been shown to increase SWA [42]. In fact, the most commonly used prescription sleep medications decrease SWA and are therefore often associated with residual daytime sleepiness despite increased sleep duration [43]. Nutritional supplements such as melatonin do not increase SWS or SWA and may decrease it [44]. Thus, there is a need for a new approach to increase the depth of NREM sleep.

Researchers at the University of Wisconsin have found that the timed delivery of auditory stimuli during sleep that are not consciously perceived can enhance SWA

throughout the night [6, 41]. The findings have led to the development of several prototype devices which have demonstrated increasingly higher performance. The goal of the present study is to test the most recent prototype, named PowerSleep, in active adults who have insufficient sleep.

RESPIRONICS

PowerSleep is a non-invasive portable light weight device designed to stimulate slowwave sleep and thereby reduce daytime sleepiness associated with insufficient sleep or poorly perceived sleep quality [45]. Auditory stimulation is provided during SWS, to compensate for insufficient sleep duration by increasing sleep intensity or to improve sleep quality by increasing sleep intensity. Sleep intensity can be objectively assessed by Slow-Wave Activity (SWA), defined as EEG spectral power in the frequency range 0.75-4 Hz. In normal individuals, a reduction in the amount of SWA consistently results in reduced alertness with impaired performance due to cognitive and memory deficits [41].

The PowerSleep device delivers acoustic stimuli that are calibrated to stimulate SWA without awakening the user. The PowerSleep device is wearable and non-invasive, consisting of a silicone headband with integrated electrodes and speakers over each ear. The headband is connected via a tether cable to a user interface which houses the EEG amplifier and electronics of the device. The headband is adjustable via a Velcro strap. The device also includes a right mastoid electrode. The device monitors and records EEG throughout the night, and is capable of on-line identification of sleep stages and continuous EEG analysis. The user interface contains the device electronics. EEG data collected by the PowerSleep device can be transferred to the computer by a technician after home use and used to assess sleep quality. Soft audio tones (below 65dB to prevent arousals from sleep) will be administered via the speakers during deep sleep throughout the night.

A pilot study with 27 participants (average age  $36.7 \pm 7.3$ , 16 female/9 male), was conducted by Philips Respironics. The study showed that it is possible to enhance slow wave sleep by using non-pharmacological methods such as auditory stimulation (AS) and that coupled with closed-loop brain activity monitoring (EEG) provided by the device provides an increase in slow wave activity by 7% which helps improve vigilance, cognitive functions, and memory, as well as subjective ratings of sleepiness, physical fatigue, and mental tiredness.

In addition, interim results (N=9) from an in-lab study conducted with the PowerSleep device, 77.8 % showed an increase in SWA ranging from 5-33%. Participants showed an improvement in cognitive outcomes following acoustic stimulation during overnight sleep. Improvements were noted in executive function task (verbal fluency), vigilance

<sup>1 Internal Philips Respironics Report- data on file

and alertness (PVT) and sleep dependent declarative memory task (Paired associates memory task).

# **II. SPECIFIC AIMS/HYPOTHESIS**

#### Primary Aim(s):

To assess the effects of the auditory stimulation delivered by the PowerSleep device in adults who are sleep restricted. Efficacy will be evaluated based on the average of two nights (2 night) use of active PowerSleep (delivering audio tones) compared to the average of two nights (2 nights) use of a sham device (delivering no audio tones).

It is hypothesized that the use of active PowerSleep, as compared to the sham device, will result in a significant increase (≥5%), in mean total slow-wave activity (SWA) over the 2 work nights of use.

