#### Secondary Aims:

To evaluate the effect of 2 nights of PowerSleep use on MSLT (sleep latency), subjective sleepiness scales, and cognitive testing.

To evaluate the relationship between MSLT (sleep latency), subjective sleepiness scales, and cognitive testing changes and changes in SWA.

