# **Determination of Sample Size**

100 participants may be screened, up to 75 participants will be enrolled (randomized) in order to ensure at least 50 complete data sets. An interim analysis (N=9) from an international study of similar design suggests that between 24-47 participants would be required to reach statistical significance for the primary endpoint of slow-wave activity (SWA).

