#### **General Considerations**

The primary analysis will include all completed participants who contributed at least one night of usable PSG data for each therapy condition. If there are participants whose therapy order is switched from their randomized assignment, then the results will be analyzed according to both the as-randomized and the as-treated assignments. If the sleep data are not usable for both nights in a given therapy, those participants will be excluded from the primary analysis, and site(s) may over-enroll to compensate for these missing data. The safety analysis will include all randomized subjects.

All variables will be summarized by descriptive statistics. The statistics for continuous variables include mean, median, standard deviation, minimum, maximum, 95% confidence interval (CI) for the mean, and number of observations. For categorical variables, frequencies and percentages will be presented. All analyses will be conducted using either SAS® or SPSS® software.

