#### **Primary Efficacy Analysis**

The primary efficacy measure for this study will be the cumulative or average slow-wave activity (SWA), which will be measured at multiple EEG electrode locations (channels). As stated in the study procedures, two PSG nights will be collected for each therapy.

The primary SWA endpoint will be the average of the two nights, but secondary analyses will include separate assessments of the first and second nights within each therapy. The data will be evaluated to determine whether they meet the assumptions of parametric methods. SWA will be compared between the Active and Sham conditions, using either a paired t-test or the nonparametric Wilcoxon Signed Ranks test, depending on the distribution of the paired differences. The comparisons will be performed within and between EEG channels. The significance level will be a two-sided alpha of 0.05, and if necessary, this will be adjusted for multiple comparisons.

RESPIRONICS

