# Interim Analysis

An interim analysis is planned when approximately 50% of the enrolled population completes the study. If the effect size observed at the interim is less than originally expected, the sample size may be increased.

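### Does the 5% named in the primary hypothesis need its own test, margin or percent-change rule?

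*Combined protocol and SAP*

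**What the plan says.** - **Primary Aim (section II).** The active device, compared with sham, "will result in a significant increase (≥5%), in mean total slow-wave activity (SWA) over the 2 work nights of use". The role of the 5% is not stated.
- **Primary Efficacy Analysis (section V).** "SWA will be compared between the Active and Sham conditions, using either a paired t-test or the nonparametric Wilcoxon Signed Ranks test", at two-sided 0.05, on the average of two nights per condition. There is no percent scale and no non-zero null value.
- **General Considerations.** All variables are to be summarised, and for continuous ones this includes a "95% confidence interval (CI) for the mean". No interval is specified for a percent change.
- **Determination of Sample Size.** An N=9 interim from a similar study suggests that "between 24-47 participants would be required to reach statistical significance for the primary endpoint". The target is at least 50 complete data sets from up to 75 randomised. No effect size, SD or power is given.
- **Interim Analysis.** "If the effect size observed at the interim is less than originally expected, the sample size may be increased". The expected effect is not given.
- **Background (section I).** The pilot study is said to show that stimulation "provides an increase in slow wave activity by 7"%. In the N=9 interim, "77.8 % showed an increase in SWA ranging from 5-33"%. Neither comes with an SD.
- **Secondary Aims.** These refer to "cognitive testing changes and changes in SWA", so changes in SWA are expected to be calculated.

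**The concern.** The hypothesis is worded in percent with a lower bound, while the test asks only whether SWA differs between conditions. A significant result could therefore be reported as meeting the hypothesis even though the observed increase is below 5%, or its confidence interval reaches well below 5%.

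Two further gaps add to this. The formula for percent change is open: it could be a ratio of means, a mean of individual changes or a geometric mean ratio. The interim rule also refers to an expected effect that has no number. If 5% were a success threshold, the plan would be testing the wrong null value and the sample size would be far too small.

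**Working it through.** **1. Can 24-47 be traced to 5%?** The plan's figure cannot be reproduced, because effect, SD and power are not given. Working backwards, I solved for the standardised paired effect d at which the two-sided 0.05 paired t-test (noncentral t) has the stated power. The SD of percent change is then effect / d.

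| n | d, 80% power | SD if effect 5% | SD if effect 7% | d, 90% power |
|---|---|---|---|---|
| 24 | 0.597 | 5/0.597 = 8.4 | 7/0.597 = 11.7 | 0.691 |
| 47 | 0.417 | 5/0.417 = 12.0 | 7/0.417 = 16.8 | 0.483 |

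The range fits either effect, so it neither confirms nor excludes 5% as the design effect. The 7%/80% case used below joins the pilot's effect to a range taken from another study. It is an illustration only.

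**2. How small can a significant increase be?** For a t-test on percent change (the plan tests SWA itself, so this is an approximation), cutoff = t(0.975, N-1)/√N × SD.

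- N=50: 2.010/√50 = 0.2842, giving 3.3% (SD 11.7) or 4.8% (SD 16.8).
- N=75: 1.993/√75 = 0.2301, giving 2.7% or 3.9%.
- The cutoff passes 5% once the SD exceeds 5/0.2842 = 17.6 points (N=50) or 5/0.2301 = 21.7 points (N=75).
- With a 15% effect behind 24-47, the N=50 cutoffs are 6.2-10.2%, and significance below 5% cannot occur on this test.

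**3. How often would significance come with an observed increase below 5%?** All at N=50, with assumed variability.

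- True 7%, lognormal SWA, between-person log-SD 0.3-0.7: 4-14% of trials by ratio of means, 0.3-4% by mean of individual changes.
- True 5%, normal percent changes: about 34% (SD 11.7) or 6% (SD 16.8); 43% at SD 10.
- True 3%: about 32%, 5% and 47% at the same three SDs.

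In each case a true increase exists, so concluding that there is an increase is correct. With no true effect, the t-test/Wilcoxon switch rejects in 4.4-5.2% of simulated trials, taking Shapiro p<0.05 as the assumed trigger for Wilcoxon.

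**4. What if 5% were made a threshold for the lower 95% limit?** On the log scale, the SD of the log ratio is ln(1.07)/d = 0.0677/0.597 = 0.1133 or 0.0677/0.417 = 0.1622. At a true 7% the distance to the threshold is ln(1.07/1.05) = 0.0189, so d is 0.0189/0.1133 = 0.167 or 0.0189/0.1622 = 0.116. The chance of success is about 21% or 12% at N=50, and 30% or 17% at N=75. On the percent scale, 80% power at a true 7% would need 128, 199, 285 or 444 participants at SDs of 8, 10, 12 or 15 points. A plan for 50 to 75 participants was not built on that reading.

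**5. Would a log-ratio primary analysis be better?** Simulated power at a 7% increase, N=50, between-person log-SD 0.3/0.5/0.7:

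| Noise | d | Planned switch | Log-ratio t-test |
|---|---|---|---|
| Multiplicative | 0.597 | 0.976/0.971/0.962 | 0.985/0.987/0.985 |
| Multiplicative | 0.417 | 0.803/0.767/0.752 | 0.831/0.822/0.831 |
| Additive | 0.597 | 0.98/0.99/0.99 | 0.98/0.95/0.92 |
| Additive | 0.417 | 0.81/0.82/0.83 | 0.78/0.71/0.65 |

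The log ratio gains about 1-8 points where noise is multiplicative, which is the model it is built for. It loses up to about 18 points where noise is additive; a separate run put the largest loss at about 21. The documents do not say which model holds.

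**The case for a change.** The best case for a change is the open formula. In lognormal simulations at a true 7% and N=50, the ratio of means and the mean of individual changes fell on opposite sides of 5% in about 7-19% of trials. Someone choosing the formula after seeing the data could thus choose whether 5% appears to be met. The descriptive intervals in General Considerations give at most an interval for the raw change. The interim rule also has no numerical comparator. Wording alone would close these gaps, with no new data.

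The gaps are real, and one sentence saying what 5% is, and how percent change is calculated, would do no harm. They do not reach the primary conclusion, though. The test does not use the percent-change formula, so significance cannot be altered by choosing one. The Primary Aim speaks of mean total SWA averaged over two nights per condition, which leans towards a percent change in means, though not decisively. The paired data allow a reader to see any of the three summaries with an interval. As for the interim, the sentence allows an increase in sample size but does not require one. How that decision should be governed is a separate question, which a label for the 5% would not settle.

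**Conclusion.** The mismatch in wording is there, but no change to the plan follows. Testing against zero while hypothesising an effect size is ordinary practice. The test is valid for an increase, and the plan nowhere claims that it proves at least 5%. Reading 5% as an expected effect is a judgement, supported by the 7% pilot and by a sample size that could not serve a 5% threshold under the variability considered. What is missing is descriptive detail that a competent analyst would supply when reporting against a percent hypothesis.

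The stronger remedies do not improve the trial. A lower-limit criterion adds a hurdle that the plan never set, cleared in roughly 12-21% of trials at a true 7% and N=50. A log-ratio primary variable is a trade-off: about 1-8 points of power gained, or up to about 18-21 lost. Every probability here rests on assumed SDs and on pairing the pilot effect with 24-47; larger SDs or effects make significance below 5% rarer or impossible. The answer would differ if 5% were meant as a success threshold, and nothing in the documents says so.

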#### Secondary Aims:

To evaluate the effect of 2 nights of PowerSleep use on MSLT (sleep latency), subjective sleepiness scales, and cognitive testing.

To evaluate the relationship between MSLT (sleep latency), subjective sleepiness scales, and cognitive testing changes and changes in SWA.

#### **III. STUDY DESIGN and METHODS**

#### A. Design:

This study is a randomized, double-blind, placebo-controlled cross-over study designed to evaluate the effectiveness and efficacy of 2 consecutive work days of nightly use of active versus sham PowerSleep devices in adults with self-imposed restricted sleep schedules. The primary analysis will be intent-to-treat with the secondary analysis as an as-treated analysis. The expected duration of the study for each participant is up to 4 weeks.

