# Subject Disposition

Subject disposition, including the total number of participant's enrolled, randomized, completed, early terminations and withdrawals, will be presented. In addition, a listing will be provided with the reasons for discontinuation.

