#### Demographics and Baseline Characteristics

Standard subject demographics (e.g., age and gender) and baseline characteristics will be summarized for all participants enrolled and for evaluable subjects.

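### The Design section calls the primary analysis intent-to-treat, but General Considerations defines an evaluable set that leaves out some randomised participants, so the label is wrong as written

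*Combined protocol and SAP*

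**What the plan says.** Section III.A (Design): "The primary analysis will be intent-to-treat with the secondary analysis as an as-treated analysis".

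Section V, General Considerations, sets out who is analysed: "The primary analysis will include all completed participants who contributed at least one night of usable PSG data for each therapy condition". For participants whose sleep data are unusable in a therapy, "those participants will be excluded from the primary analysis, and site(s) may over-enroll to compensate for these missing data". If therapy order was switched from the randomised one, "then the results will be analyzed according to both the as-randomized and the as-treated assignments". The whole randomised group is named only for safety: "The safety analysis will include all randomized subjects".

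Other sections bear on the same point:

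- Demographics and Baseline Characteristics: these are to be "summarized for all participants enrolled and for evaluable subjects", so the plan itself separates an evaluable set from the enrolled one.
- Determination of Sample Size: "up to 75 participants will be enrolled (randomized) in order to ensure at least 50 complete data sets". The Study Participants section words the 75 differently, as the number who may complete.
- Subject Disposition: "a listing will be provided with the reasons for discontinuation".
- Withdrawal Criteria (section VI): discontinuation means leaving the study before every procedure is done.
- Opening of section V: blinded scorers judge data quality, and the usability criteria are still to be set but will be applied consistently.
- Treatment Compliance: drop-out is expected to be low. No rate is given.

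**The concern.** A reader who sees *intent-to-treat* takes the primary result to cover everyone randomised, grouped as randomised. The set actually defined meets the second half of that description but not the first. If the trial is reported under the Design label, the report will claim a protection against selective loss that the analysis does not provide.

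Two details of wording add to this. First, *completed* stands as a condition on top of the usable-night requirement and is not defined. The last study night comes before about eight hours of daytime testing (Overnight in-lab visit 5). Someone who leaves that morning has already supplied the primary endpoint, yet might be counted as not completed. Second, the exclusion for sleep data unusable on *both nights* can mean that neither night is usable, or that the two are not both usable. Only the first meaning agrees with the one-night minimum stated earlier in the same paragraph.

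Loss could in principle depend on treatment, because the risk section says that stimulation can fragment sleep. The planned listing covers discontinuations. It does not mention participants excluded for unusable nights, so that loss might not be visible in the report.

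**Working it through.** **1. Who is in under each text.** Intent-to-treat is taken in its usual sense: all randomised, grouped as randomised.

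| Randomised participant | Design label | General Considerations | After the fix |
|---|---|---|---|
| Usable SWA in both conditions, all procedures done | in | in | in |
| At least one usable night in each condition, leaves before the last daytime testing | in | unclear: depends on *completed* | in |
| One usable night of two in a condition | in | in by the one-night minimum; out if *both nights* means not both usable | in |
| No usable night in one condition | in | out | out, but tabulated |
| Order switched, data usable | in, as randomised | in, reported both ways, ranking not repeated | in, as-randomised primary |

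The fourth row alone establishes the conflict. The second and third rows are ambiguities, and the fifth is a missing cross-reference.

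**2. Whether other text restores the excluded.** The as-randomised rule applies only to switched orders. Over-enrolment adds new participants and does not bring back those excluded. No missing-data method is given for the primary analysis. So nothing turns the defined set into the labelled one.

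**3. How many could be affected.** From Determination of Sample Size, 75 − 50 = 25, and 25/75 = 0.333, or 33%. This sets a maximum (75 randomised) against a minimum (50 complete sets), so it is the upper end of what the plan allows for. The lower end is zero. The documents give no expected rate of drop-out or of unusable nights, and no basis for counting the second-row participants.

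**4. Precision.** The plan puts the number required at 24 to 47. That range cannot be reproduced, because neither the power nor the standard deviation of the paired differences is given, and this point does not depend on it. The target of 50 exceeds the upper figure by 50 − 47 = 3, so by the plan's own figures exclusions down to 50 would not leave it short. What is at issue is whom the result describes.

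**5. Bias.** For the mean effect, retained minus all randomised = (share excluded) × (mean effect in retained − mean effect in excluded). The documents bound the first term at 33% and say nothing about the second. No numerical shift can be derived from them, and none is offered.

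**The case against.** The best defence is that *intent-to-treat* meant only *by randomised order*. The Design sentence contrasts it with as-treated, which is a contrast of assignment, and General Considerations carries the same contrast into its switched-order rule. The paired test in Primary Efficacy Analysis cannot use a participant who lacks one condition, and General Considerations states openly who is included. Blinded scoring, the listing of discontinuation reasons and baseline summaries for both sets are real safeguards.

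Most of this stands as an explanation of how the wording arose. It does not make the label accurate, since a reader of the Design section would still be told something that the statistical section contradicts. It does show that the paired test should stay and that the description should change.

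Three stronger readings might be inferred, and the documents do not support them:

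- *The plan never says which assignment is primary.* It does. The Design sentence puts the as-randomised analysis first and as-treated second. General Considerations only fails to repeat this.
- *Participants who miss the final daytime testing will be dropped.* General Considerations does not refer to Withdrawal Criteria, and missing one procedure is not plainly withdrawal. This is a possible reading of an undefined word, not a stated rule.
- *A third of those randomised will be lost, or the result will be biased.* The 33% is a ceiling, low drop-out is expected, and nothing shows that loss depends on treatment.

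**Conclusion.** The conflict in the text is certain: the primary set is evaluable participants, and the intent-to-treat label is wrong as written. It should be fixed, because the label governs how the main result will be described and because an undefined *completed* leaves room to discard primary data already collected.

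This confidence applies to the wording only. The direction and size of any bias are unknown, and the effect is probably small if drop-out is as low as Treatment Compliance expects. The correction would not bring participants without a usable night in one condition into the primary analysis. It makes their exclusion explicit and countable.

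**What to change.** Before unblinding:

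1. In General Considerations, define the primary set as *all randomised participants with at least one usable PSG night in each condition, whether or not they completed other procedures*, and drop the separate completion requirement.
2. In Design, replace the intent-to-treat label with *evaluable, analysed as randomised*, keep as-treated as secondary, and repeat that order in General Considerations for switched sequences.
3. Reword the exclusion for unusable sleep data to *neither night usable in a given therapy*, so that it matches the one-night minimum.
4. Tabulate exclusions from the primary analysis by condition and reason, including unusable nights as well as discontinuations.

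Keep the paired t-test or Wilcoxon test as primary. A mixed model on all usable nights from all randomised participants is an optional sensitivity analysis. It assumes that data are missing at random, relies on approximate normality, and gains little from participants who have one condition only.

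The cost is a few sentences and one table, with no added participants or visits. The downside is a less favourable label and slightly more reporting work.
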